**Categorical description of time effect on  $\Delta$ QTcF**

The standard model contains a categorical variable to account for time dependent changes in QTc ( $\theta_{2,k} * TIME_{i,k}$ ). This parameterization is agnostic to any trends in such changes, and may be better represented by other functions. In particular, it has been reported in literature that (co)sinusoidal functions may describe the change in QTc due to diurnal / circadian variation, e.g. Koch & Raschka 2002 [5]. Inspection of the Day -1 serial QTc data may help to elucidate such trends in change of QTc over time and drive the specification of such a time-dependent function.

**4.9.2.2 Model evaluation**

Diagnostic and goodness of fit plots will be presented for the final model and will include:

- Quantile-Quantile plots of residuals;
- Concentrations versus residuals;
- Time and baseline versus residuals;
- Model predicted  $\Delta$ QTc versus observed  $\Delta$ QTc plotted with a loess line.
- Mean observed and predicted  $\Delta$ QTc by deciles of concentrations (quantile plot) with model slope and 90% CI.

#### 4.9.2.3 Summary of measure

Individual Cmax values for participants at the 60 mg dose will be used to calculate the Cmax geometric mean. Based on the estimated model, the calculated geometric mean Cmax for dose 60 mg will be used in the fitted model to predict the upper limit of the 90% CI of  $\Delta QTc$  at dose 60 mg as follows (in the case of a linear model):

$$\overline{\Delta QTc_{60mg}} = \theta_0 + \theta_1 Cmax(60mg)$$

$$90\% CI = \overline{\Delta QTc_{60mg}} \pm t(0.95, DF) \times SE$$

$$SE = \sqrt{var(\theta_0) + C_{max}^2(60 mg) var(\theta_1) + 2C_{max}(60 mg) \times cov(\theta_0, \theta_1)}$$

Where:

- $\overline{\Delta QTc_{60mg}}$  is the predicted  $\Delta QTc$  at 60 mg;
- $\theta_0$  is the estimated fixed intercept term;
- $\theta_1$  is the estimated fixed slope for concentrations;
- $t(0.95, DF)$  is the 95th quantile from the student distribution with  $DF$  degrees of freedom;
- SE is the standard error ;
- $var(\theta_0)$ ,  $var(\theta_1)$  and  $cov(\theta_0, \theta_1)$  are respectively the variance of  $\theta_0$  and  $\theta_1$  and their covariance.

The summary measure of the study is the geometric mean and 90% CI of the predicted  $\Delta QTc$  at 60 mg Cmax. If the upper bound of 90% CI for this predicted  $\Delta QTc$  falls below the 10 msec mark, the conclusion of the study is that there is no clinically relevant QTc prolongation up to and including the 60 mg dose. In case the upper 90% CI limit does not fall below the 10 msec mark, the same evaluation will be performed for the  $\Delta QTc$  at the geometric mean Cmax of the 40 mg once daily dose.

#### 4.9.3 Handling of Intercurrent Events

The following intercurrent event will be considered:

- a. Treatment discontinuation due to any reason - While on-treatment strategy will be applied to address this intercurrent event.  
The data affected by occurrence of the intercurrent event would be treated as missing at random from the occurrence of the intercurrent event until the end of the study. Participant level missing data considered as missing at random, will not be imputed and available data will be used in the primary analysis.
- b. Any events affect the drug absorption (1 hour) – Treatment Policy strategy will be applied to address this intercurrent event for the estimation model as it is based on concentration not dose - therefore even though the concentration may be affected, the data is still relevant for quantifying the relationship between change in QTc and drug concentration. Hence, we will use all the data in the modelling (paroxetine concentration and  $\Delta QTc$ ) irrespective of the occurrence of the intercurrent event. However, when the model is used to predict the upper 90% CI for 60mg doses an absorption event may artificially reduce the prediction, hence the corresponding paroxetine concentration data will not be used in the calculation of the Cmax at and in the prediction of the geometric mean of predicted  $\Delta QTc$  and 90% CI.

#### 4.9.4 Handling of Missing Values not Related to Intercurrent Event

Missing data not related to intercurrent event will not be imputed and available data will be used in the primary analysis.

#### 4.9.5 Sensitivity analyses

A sensitivity analysis will be performed to ensure that there is no bias in the calculated geometric mean of the Cmax at the 60 mg once daily dose, in case:

- Twenty percent (20%) or more of the total PK data is missing, or
- Twenty percent (20%) or more of participants (8 participants or more) at the 60 mg once daily dose have either missing paroxetine concentration data around the Cmax at the 60 mg dose level, or an intercurrent event of “any events affecting absorption within 1 hour of the dose” at the 60 mg dose

This analysis will consist of a population pharmacokinetic (PopPK) model-fitting of the individual paroxetine concentration data without the estimation of population level parameters (post-hoc or Bayesian fit), using a paroxetine popPK model developed internally at GSK. Appropriateness of the available paroxetine popPK model will be determined based on goodness-of-fit plots (e.g. population and individual prediction [PRED, IPRED] vs observed concentrations [DV], CWRES vs IPRED). A description of the popPK model, if used for sensitivity analysis, will be included in the study report.

The individual PK parameters from the Bayesian model fit will allow the model-based individualised prediction of the Cmax at the 60 mg once daily dose for those participants with missing data, based on the available paroxetine concentration data at the earlier doses. Through this method, a geometric mean of Cmax at the 60 mg dose can be calculated that should be less affected by dropout, missing data, or intercurrent events. An additional calculation of the upper limit of the 90% CI of  $\Delta QTc$  will then be performed using the Cmax of the 60 mg dose calculated using this method. In case the evaluation of  $\Delta QTc$  finds a  $\geq 10$  ms upper 90% CI limit at the 60 mg dose, the same model-based prediction of Cmax at the 40 mg dose for dropouts will be performed, where required. If such a sensitivity analysis is performed, results from both the regular analysis (without PK model fitting and predictions) and the sensitivity analysis will be presented in the study report.

#### 4.9.6 Supplementary analyses

Not applicable.

### 4.10 Analysis Supporting Secondary Objective(s)

Analysis Supporting secondary Objective are described in section 4.12.

### 4.11 Pharmacokinetic Analysis, Concentration, and Parameter TFLs, and Statistical Analysis of Pharmacokinetic Parameters for Final Analysis

#### 4.11.1 Pharmacokinetic Concentrations

##### Concentration Listings:

Pharmacokinetic concentration data for paroxetine will be listed by participant for the Safety analysis set. Concentration listings will include nominal PK sampling time, actual sampling times relative to dose administration, deviation from nominal time, and percent deviation from nominal time, and concentrations. Plasma concentrations below the lower limit of quantification (LLOQ) will be presented as below the lower limit of quantification (BLQ) in the listings and the LLOQ value presented as a footnote. Missing PK samples will be reported in the (blinded) data review meeting report (see section 4.4.3) and not reportable samples will be reported as NR, in listings and considered excluded from PK analysis.

**Concentration Summary Tables:**

Source data as reported from the laboratory will be used for calculation of concentration summary statistics. Tabular summaries for concentration-time data will report N (number of subjects included in the PK population for each dose), n (number of subjects at a given timepoint), and n(BLQ) (the number of subjects with BLQ samples).

Concentration for paroxetine will be summarized by dose, and nominal timepoint for the PKAS. The following descriptive statistics will be presented for plasma concentrations obtained at each nominal time point: N, n, n(BLQ), arithmetic mean, SD, coefficient of variation (CV%), geometric mean, geometric CV% (calculated as:  $gCV\% = \text{SQRT}(e^{s^2} - 1) * 100$ ; where s is the SD of the log-transformed values), 95% CI, median, minimum, and maximum values.

For summary tables, all BLQs will be replaced with zero except when an individual BLQ falls between two quantifiable values, in which case it will be omitted for the calculation of all summary statistics. For the calculation geometric mean and geometric CV%, BLQ values will be replaced by half the LLOQ value instead of zero. Summary statistics will not be calculated if non-BLQ concentrations at a scheduled time point is <3 and will be reported as NC, with the exception of minimum and maximum; minimum will be reported as “BLQ” and in case of all BLQ values, also maximum will be reported as “BLQ”.

The rules followed for calculation and presentation of concentration data with regards to the number of decimal places/significant digits for the listings of participant level concentrations and summary tables of concentration are as follows:

Concentration Listings and Tables	Rounding
Individual concentrations	n s.f. as supplied by bioanalytical laboratory
Minimum and Maximum	n s.f. as original data
Mean/Median/Geomean	3 s.f.
SD, CI	4 s.f.
CV%/gCV%	1 d.p.
N/n	Whole number

s.f = significant figures, d.p. = decimal place

**Concentration Figures:**

For arithmetic or geometric mean linear/linear graphs, the data plotted in the figure should match the data presented in the summary table, with the exception of values reported in table as NC prior to  $C_{\max}$  which should be set to 0 in the figure (to capture lag-time). For arithmetic or geometric mean log/linear graphs, all values reported in table as NC will be set to missing.

For individual linear/linear and log/linear graphs all BLQ values will be substituted as follows:

- One or more BLQs at the beginning of a participant profile (i.e., before the first incidence of a measurable concentration) will be assigned to zero. When using semilog scale, these timepoints will be considered missing.
- BLQs at the end of a participant profile (i.e., after the last incidence of a measurable concentration) will be set to missing.

- Single BLQs which fall between two measurable concentrations will be set to missing.
- More than one consecutive BLQs which fall between measurable concentrations will be set to zero, and the subsequent measurable concentrations will be retained.

To visualize participant-level concentrations and the comparison between groups for each dose, the descriptive PK graphs listed below will be generated. Include LLOQ line in individual and summary plots.

- Individual participant profiles for paroxetine plasma concentration time data – (linear scale and semi-logarithmic scale) (SAF)
- Overlaid individual participant profiles for paroxetine Plasma Concentration Time Data – (linear scale and semi-logarithmic scale) (SAF)
- Mean ( $\pm$  SD) paroxetine plasma concentration time data – (linear scale and semi-logarithmic scale) (PKAS)
- Median (range) paroxetine plasma concentration time data – (linear scale and semi-logarithmic scale) (PKAS)

Figures will be generated in black and white using unique line style and marker for each plot in the graph. For all PK concentration-time plots, a linear scale will be used for the x-axis (e.g., not an ordinal scale).

#### 4.11.2 Pharmacokinetic Parameters

PK parameters will be provided by Parexel CPMS group. PK parameters will be calculated by NCA methods from the concentration-time data using Phoenix® WinNonlin® Version 8.3 or higher following these guidelines:

- Actual time from dose will be used in the calculation of all derived PK parameters, except when parameters are calculated for safety/dose escalation meetings when nominal times may be used to calculate PK parameters.
- Handling of BLQ samples for derivation of plasma PK parameters after each dose administration
  - BLQs at the beginning of a participant profile (i.e., before the first incidence of a measurable concentration) will be assigned to zero.
  - BLQs at the end of a participant profile (i.e., after the last incidence of a measurable concentration) will be set to missing.
  - Single BLQs which fall between two measurable concentrations will be set to missing.
  - Consecutive BLQs which fall between measurable concentrations will be set to missing. Measurable concentrations after consecutive BLQs will also be set to missing.

Pharmacokinetic parameters will be estimated according to the guidelines presented in [Table 4-1](#).

**Table 4-1 Pharmacokinetic Parameter and Estimation**

Parameter	Guideline for Derivation
$C_{\max}$ , $t_{\max}$	Obtained directly from the observed concentration-time data, unless specified otherwise (see Section 4.9.1 ).

**PK Parameters Listings:**

PK parameters will be listed by participant for the SAF. PK parameters that will be flagged and/or excluded from summary tables and statistical analyses of PK parameters will be flagged and footnoted with the reason for flagging/exclusion.

**PK Parameter Summary Tables:**

Biostatistics group will consider the derived PK parameters as source data and will use this data without rounding for calculation of PK parameters summary statistics tables.

PK parameters will be summarized by treatment for the PK Set.

Tabular summaries for PK parameters will report N (number of subjects included in the PK population for each dose) and n (number of subjects with a specific parameter).

Descriptive statistics for calculated PK parameters will include N, n, arithmetic mean, SD, CV%, geometric mean, gCV%, 95% CI, median, minimum, and maximum values. For  $t_{max}$ , only N, n, median, minimum, and maximum values will be presented. No descriptive statistics will be determined when fewer than three individual PK parameters are available.

The rules followed for presentation of PK parameters data with regards to the number of decimal places/significant digits for the listings of participant level PK parameters and summary tables of PK parameters are as follows:

PK Parameter Listings and Tables	Rounding
Derived Individual parameters	3 s.f.
Directly Derived Individual parameters ( $C_{max}$ )	$n$ s.f. as supplied by the analytical laboratory but not more than 3 s.f.
Minimum and Maximum	3 s.f.
Mean/Median/Geomean	4 s.f.
SD	5 s.f.
CV%/gCV%	1 d.p.
Comparative estimates (e.g. ratios)	3 d.p.
CI and other percentages	4 s.f.
p-values	4 d.p.
N/n	Whole number
Exceptions for PK Tables	
$t_{max}$ individuals and min/max	2 d.p
$t_{max}$ median only	2 d.p

s.f = significant figures, d.p. = decimal place

#### 4.12 Safety Evaluation

Secondary estimands address all other safety and tolerability findings.

Treatment policy strategy will be applied for Study treatment discontinuation due to any reason intercurrent event - Safety data will be monitored throughout the study after the start of treatment. There is interest in evaluating and reporting safety events regardless of whether participants discontinued treatment.

All safety analysis will be performed on the Safety Set. All participants who received treatment of study medication will be included in the safety analysis. Categorical data will be summarized using counts and percentages, however continuous data will be summarized using descriptive statistics (number of observations, mean, standard deviation, median, minimum, and maximum for continuous data by dose).

#### 4.12.1 Adverse Events

An AE is any untoward medical occurrence in a clinical study participant, temporally associated with the use of a study intervention, whether or not considered related to the study intervention.

All outputs for Adverse Events (AEs) will be based on the Safety Set unless specified separately in TLF shells.

Summaries of AEs will include the following:

- Incidence of AEs - Overview by dose and overall
- Incidence of AEs by dose, SOC, and PT
- Incidence of AEs by maximum causality, dose, SOC, and PT)
- Incidence of AEs by maximum intensity by dose, SOC, and PT)
- Adverse Events (AEs) Leading to discontinuation of study intervention by dose, SOC and PT
- Incidence of SAEs - Overview by dose and overall
- Incidence of SAEs by dose, SOC, and PT
- Summary of common ( $\geq 5\%$ ) non-serious adverse events (not included in the serious of adverse event) - Number of subjects and occurrences by SOC & PT
- Summary of drug related any adverse events – Number and percentage of subjects by SOC & PT
- Summary of fatal adverse events – Number and percentage of subjects by SOC & PT
- Summary of drug related fatal adverse events – Number and percentage of subjects by SOC & PT
- Summary of drug related non-serious adverse events - Number and percentage of subjects by SOC & PT

All TEAE summaries should provide the number and percentages of subjects reporting at least one TEAE and the total number of events reported.

Summaries of TEAEs will include the following:

- Incidence of TEAEs - Overview by dose and overall
- Incidence of TEAEs by dose, SOC, and PT

Summary tables will contain counts of participants, percentages of participants in parentheses, and the number of events where applicable. A participant who has multiple events in the same SOC and PT will be counted only once in the participant counts, but all events will be included.

A listing will be created for all Adverse Events (AEs), which will include study day, preferred term (PT), system organ class (SOC), AE onset date (and time), AE end date (and time) or ongoing,

duration of the AE, causal relationship to IMP, AE outcome, intensity and seriousness, action taken with IMP, concomitant medication (if administered), and TEAE indicator flag.

Adverse event summaries will be ordered in terms of decreasing frequency for SOC, and PT within SOC, and then alphabetically for SOC, and PT within SOC.

Adverse events will be coded using Medical Dictionary for Regulatory Activities (MedDRA®), Version 26.0 or higher).

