**CONFIDENTIAL****Protocol and Version 2.0 (Final)**

|  |   |  |
|--|---|--|
| Symptoms seen on discontinuation of paroxetine | 
In clinical trials in adults, adverse events seen on treatment discontinuation occurred in 30% of patients treated with paroxetine compared to 20% of patients treated with placebo.
 
Common adverse events which can occur following discontinuation of treatment with paroxetine include: dizziness, sensory disturbances, sleep disturbances, anxiety and headache. Adverse events including agitation, nausea, tremor, confusion, sweating and diarrhoea have also been reported uncommonly after discontinuing paroxetine treatment.
 
Discontinuation type symptoms are most likely to occur on abrupt discontinuation of paroxetine but have also been seen during the dose taper phase of treatment. Generally, these symptoms are self-limiting and usually resolve within 2 weeks, though in some individuals they may be prolonged (2-3 months or more).
 
It is recommended that paroxetine should be gradually tapered when discontinuing treatment over a period of several weeks or months.
 | 
After the study dosing period (up to 60 mg daily) participants will be undergoing gradual tapering of their paroxetine dose in decrements of 20 mg over a total tapering period of ten days. Refer to section 1.2, Schema.
 
Participants should be made aware of the type of symptoms which might occur during the tapering phase.
 
Withdrawal symptoms generally tend to be self-limiting. However, based on PI's clinical assessment of withdrawal symptoms during the tapering phase of 20 mg OD to no paroxetine, an additional 5 days of 10 mg OD paroxetine may be provided.
 
In addition, withdrawal symptoms may be treated, at the PI's discretion, as clinically indicated.
 |
|--|---|--|

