## 2.2 Secondary Objective

- To assess the safety and tolerability of paroxetine doses of 20, 40, and 60 mg once daily in healthy adults.

- **Secondary Estimand:**

Secondary estimand address all other safety and tolerability findings.

The estimand is described by the following attributes:

- Population: Healthy participants of age 18 to 65 years
- Treatment condition: Dose up and down titration of paroxetine doses of 20, 40 and 60 mg
- Endpoint:
  - Occurrence of adverse events (AEs) and serious adverse events (SAEs)
  - Changes in vital signs (blood pressure, heart rate and oral body temperature) from baseline
  - Changes in hematological and clinical laboratory tests from baseline
- Summary measure: Proportions for AEs and SAEs and means of the change from baselines for vital signs, hematological, and clinical laboratory across all dose levels.
- Intercurrent events: Study intervention discontinuation due to any reason – treatment policy strategy will be applied for this intercurrent event.
- Rationale for Estimand: Safety data will be monitored throughout the study after the start of study intervention. There is interest in evaluating and reporting safety events regardless of whether participants discontinued study intervention.

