#### 4.2.1 Treatment

All participants will receive active treatment with paroxetine tablets once daily with titration steps every week over a maximum treatment period of 3 weeks. This is followed by tapering over the subsequent period of 10 days:

- Days 1-7: 20 mg once daily
- Days 8-14: 40 mg once daily
- Days 15-21: 60 mg once daily
- Days 22-26: 40 mg once daily
- Days 27-31: 20 mg once daily. If participants are not able to withdraw from 20 mg once daily directly due to withdrawal effects, an additional tapering dose step of 10 mg once daily may be given for 5 days. Unplanned visits (if needed) will be scheduled for participants who need to visit to clinic due to AEs during home dosing or required to start intermediate tapering dose of 10 mg to be started (for both clinic and home dosing) during the tapering period.
- Day 32 (or 37) onwards: complete stop of paroxetine

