#### 4.2.6 Summary and Representation of Data

Continuous data will be summarized in terms of mean, standard deviation (SD), median, minimum, maximum, and number of observations, unless otherwise stated.

Categorical data will be summarized in terms of the number of participants providing data at the relevant time point (n), frequency counts, and percentages.

The minimum and maximum will be reported to the same number of decimal places as the raw data recorded in the database. The mean and median will be reported to one more decimal place than the raw data recorded in the database. The SD will be reported to two more decimal places than the raw data recorded in the database. In general, the maximum number of decimal places reported shall be four for any summary statistics.

Percentages between 1% and 99%, inclusive, will be rounded to integers. Percentages greater than 0%, but less than 1%, will be reported as <1%, and percentages greater than 99%, but less than 100%, will be reported as >99%. If for any summary table, n is less than three then only n, minimum, and maximum should be presented, and other summary statistics will be left blank.

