#### 4.4 Study Participants

##### 4.4.1 Analysis Sets

Analysis Set	Definition / Criteria	Analyses Evaluated
Screened	
 
• All participants who were screened for eligibility
 
	
 
• Study Population
 

Enrolled	
 
• All participants who entered the study (who successfully passed screening)
 
• Note screening failures (who never passed screening even if rescreened) and participants screened but never enrolled into the study (Met eligibility but not needed) are excluded from the Enrolled analysis set as they did not enter the study.
 
	
 
• Study Population
 

Safety/Exposed	
 
• All participants who received at least one dose of study intervention.
 
	
 
• Safety
 

Analysis Set	Definition / Criteria	Analyses Evaluated
	
 
• Data will be reported according to the actual study intervention.
 
	
PK	
 
• All participants in the Safety analysis set who had at least 1 non-missing PK assessment (non-quantifiable values will be considered as non-missing values).
 
• Data will be reported according to the actual study intervention.
 
• Used for some displays required by EudraCT. Studies with single arm should use the text “Assigned rather than Randomized”.
 
	
 
• Primary analysis
 

PD	
 
• All participants in the Safety analysis set who had at least 1 non-missing ECG assessment.
 
• Data will be reported according to the actual study intervention.
 
	
 
• Primary analysis
 

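### Do the by-dose adverse-event tables need a written rule for events that start during the taper?

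*SAP*

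**What the plan says.** SAP 4.12.1 lists five AE, two SAE and two TEAE tables by dose, among them "Incidence of AEs by dose, SOC, and PT". The three overviews also have an overall column. Neither that section nor the TEAE definition after it says whether an event belongs to the dose at onset, to the last dose taken or to a period of the study. SAP 4.4.1 says of the Safety Set "Data will be reported according to the actual study intervention".

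SAP 4.2.1 describes treatment "with titration steps every week over a maximum treatment period of 3 weeks" and then a 10-day taper that begins with "Days 22-26: 40 mg once daily". It also allows a 10 mg step. The safety estimand in SAP 2.2 covers both phases: "Treatment condition: Dose up and down titration of paroxetine doses of 20, 40 and 60 mg". Its summary measure for AEs and SAEs is a proportion taken over all dose levels together.

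Protocol 2.3.1 expects discontinuation symptoms and says that they "have also been seen during the dose taper phase of treatment". Protocol 8.4 collects AEs from first dose to last visit.

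**The concern.** A column headed 20 mg or 40 mg can mean two things. If it holds every event with onset on that dose, it mixes the up-titration week with days on which the participant has just stepped down from a higher dose, so a step-down symptom would count against the lower dose. If it holds up-titration only, taper events have no dose column, although the estimand includes the taper.

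Two programmers following the SAP could therefore produce different by-dose tables. Safety and tolerability of the three doses is the only secondary objective, and Protocol 2.3.1 makes taper-phase events foreseeable. At stake would be how a reader compares tolerability between doses.

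**Working it through.** **Inputs.** Dosing days come from SAP 4.2.1, the follow-up interval from Protocol Table 1 (9 to 14 days after the last dose), the discontinuation-event rate from Protocol 2.3.1, and the sample size and dropout scenario from SAP 4.16. Day counts are for a participant who completes the schedule without a 10 mg step.

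**Reproducing the plan's taper length.** Days 22-26 give 5 days and Days 27-31 give 5 days; 5 + 5 = 10, as the SAP states. Up-titration is 7 + 7 + 7 = 21 days, so dosing lasts 21 + 10 = 31 days.

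**Columns defined by dose at onset.**

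| Dose | Up | Taper | Total | Taper share |
|---|---|---|---|---|
| 20 mg | 7 | 5 | 12 | 5/12 = 42% |
| 40 mg | 7 | 5 | 12 | 5/12 = 42% |
| 60 mg | 7 | 0 | 7 | 0% |

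**Columns defined as up-titration only.** 10/31 = 32% of dosing days have no dose column.

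**Events without a 20, 40 or 60 mg column under either definition.** These are events during a 10 mg step and events after the last dose. The off-drug days are 9/(31 + 9) = 22.5% to 14/(31 + 14) = 31% of the AE window. The two definitions are not the only ones open: a separate taper column, or carrying taper events to 60 mg, would also fit the text. All of this is one missing attribution rule.

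**How many participants.** Protocol 2.3.1 reports that "adverse events seen on treatment discontinuation occurred in 30% of patients treated with paroxetine compared to 20% of patients treated with placebo". Assuming that rate applies to these volunteers:

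- All 36 participants: 0.30 × 36 = 10.8.
- Those left at 60 mg in the SAP's dropout scenario: 36 × 0.80 × 0.75 = 21.6, and 0.30 × 21.6 = 6.5.
- The excess over placebo, all 36: (0.30 − 0.20) × 36 = 3.6.

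None of these is a count of taper-onset events. The protocol does not say what share begins during a taper, and it says such symptoms are most likely after abrupt stopping. The shares of days above are not shares of events either.

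**What depends on the rule.**

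- The estimand's AE and SAE proportions do not: the three overviews have an overall column, and neither AE collection nor the TEAE definition stops at the end of up-titration.
- SAP 4.12.1 and 4.12.2 also plan tables by system organ class and preferred term that are not split by dose, including SAEs, drug-related AEs and common non-serious AEs. These do not depend on it.
- The AE listing carries study day, onset date and time, intensity and causality (SAP 4.12.1), and the exposure listing carries dose, date and time (SAP 4.8.1). Any event can be placed in its phase.
- The primary model uses concentration and QTc from Days -1, 7, 14 and 21, so AE attribution does not enter it.
- The by-dose columns do. Of the nine tables, 9 − 3 = 6 state no overall column. The SAE table has an undivided counterpart in SAP 4.12.2. The other five do not have a full one.

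**The case for a change.** The best argument for amending the SAP is that the rule is cheap to write and nothing else supplies it. SAP 4.12.1 mentions the table shells only for exceptions to the analysis set, so the SAP does not hand this rule to them. The wording in SAP 4.4.1 reads as an ordinary as-treated statement and does not fix dose at onset. The maximum-intensity and maximum-causality tables exist only by dose, so under an up-titration-only definition taper events would be absent from both. The listings allow a later re-sort, but they do not stop two programmers from building different tables.

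The missing sentence stands, and so does its effect on those tables. Three points limit its weight.

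- The up-titration-only definition is the weaker one. It rests on a phrase describing the schedule, while SAP 4.2.1 lists Days 1-31 under treatment and SAP 2.2 includes down-titration.
- Pooling the two phases of a dose does not contradict the estimand, which pools all doses anyway.
- The obvious written rule, fixed study-day windows, would itself misplace events. Protocol 6.6 lets a participant who discontinues early step down by 20 mg every 5 days. Someone who leaves 40 mg after Day 10 and takes 20 mg from Day 11 would have taper events counted in a Day 8-14 up-titration column. Sound attribution works from actual dosing records, as an analyst would do when setting up the columns.

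Denominators are similar. SAP 4.2.6 has a general convention for categorical data, "the number of participants providing data at the relevant time point (n), frequency counts, and percentages". It does not define an AE denominator by period, but it points to counting those who contribute to the column.

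**Conclusion.** SAP 4.12.1 does not say how an event is attributed to a dose when 20 mg and 40 mg occur in both phases, or where events on 10 mg or after the last dose appear. This is missing detail in descriptive tables, which analysts fill sensibly when they define columns. It does not call for a change to the plan.

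The affected span is 5 of 12 days in each of the 20 mg and 40 mg columns, or 10 of 31 dosing days, depending on the definition. The number and direction of displaced events are unknown, and the protocol's 30% rate cannot settle it.

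The conclusion rests on two assumptions: that the overall columns include taper and follow-up events, as the estimand and the AE collection window imply, and that the report labels what its dose columns contain. With those, the secondary estimand, the listings and the primary QTc conclusion stand with the plan followed as written.
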